# Selection of donors and preparation of stool extract for FBT:

The selection and assessment of donors will be performed after obtaining a written informed consent from them (see Appendix 1) and in accordance with Guidelines for faecal bacteriotherapy (version May 2018, issued by Czech Society of Infectious Diseases, https://www.infekce.cz/DPFMT18.htm). The donors will be recruited mainly but not exclusively from volunteers donating their stool samples for another trial (Gojda et. al., NCT No), looking at the difference of intestinal microbioma between vegans and omnivores. We will only recruit donors into this study from the omnivorous cohort. After filling a pre-specified questionnaire (see Appendix 2), detailed history and physical examination will be performed.

Afterwards, the standardized donor work-up will include:

- Blood: full blood count incl. WBC differential, Sedimentation Rate, CRP, liver function tests (ALT, AST, ALP, GMT, bilirubin), creatinine, albumin and level of glucose, HIV (p24 and anti HIV-1 and 2), syphilis serology (RRR or TPPA) and hepatitis panel (HBsAg, anti-HBc IgM and IgG, HBeAg, anti-HBc total, anti-HCV, anti-HAV, anti-HEV)
- Stool examination: C.dif. (GDH and toxin A and B), cultivation to detect Shigella, Campylobacter, Listeria, Pseudomonas, Enteropathogenic E.coli (EPEC, EAEC, ETEC, EIEC), Yersinia and Salmonella sp., Vibrio cholerae, MDRO (VRE, ESBL, CRE), standard microscopy parasitological exam (Giardinia lamblia, Cryptosporidium parvum, Isospora, Microsporidia, Entamoeba histolytica) and from virological exam will be performed PCR CMV, Rotavirus, Norovirus. Fecal occult blood test.
- Nasopharyngeal swab PCR to rule out COVID-19 infection
   Culture based assay MRS

The aim of the basic blood test is to confirm the patient's good clinical condition. The aim of other tests is to prevent the transmission of latent infection from the donor to the recipient. This complete examination of the donor is repeated after 2 months. If the following examination is also found to be physiological (ie without signs of the donor's infectious disease), the stool donated by the donor during these 2 quarantine months (frozen in the stool bank) will be considered non-infectious and can be used for the FBT method. Despite this quarantine measure, the donor is obliged to fill in a questionnaire focusing on the risks of infectious diseases during each delivery of stool. In case of a new occurrence of infectious manifestations (especially diarrhea) travelled abroad or taken antibiotics the stool donor is obliged to inform about this attending physician.

22.9.2021 Protocol version 9.2

## Stool collection from the donor:

For better timing of defecation, the donor will use glycerine suppositoria (Suppositoria Glycerini 2,06g). The stool will be captured via Fe-Col Faecal Collection paper (Eastoport) and transported in a sterile container (container 2000ml, Sarsted) to the place of processing as quicly as possible, but no later than 4 hours from defecation.

# Preparation of stool extract:

The stool will be processed as soon as possible, but no later than 6 hours after defecation. The stool is weighted and mixed (hand blender, Mulinex) with normal saline 1:3, mixed thoroughly and filtered through 2 layers of gauze to remove solid parts. Afterwards, glycerine will be added to final concentration 10% and the final micture is divided into 50 ml sealed containers, labelled and immediately stored at -80 C for up to 12 months.

In order to minimise the homogeneity of the transplantate, 2 hours before transplantation, 7 aliquotes from 7 donors will be thawed at 37C water bath and drawn into the irrigation syringes/bags. Immediately afterwards, the extracts must be drawn into a sterile syringe and the resulting transplant administered to the recipient. Re-freezing of thawed or partially thawed extract is not permitted. The use of frozen stool does not reduce the effectiveness of faecal bacteriotherapy if the used graft is stored at -80 ° C for a maximum of 12 months.

#### Sample study size:

We plan to randomise 36 patients in 1:1 ratio: This is a pilot trial, with primary outcome being feasibility and safety of faecal bacterial transplantation in the population of critically ill adults with C. dif. positivity and diarrhoea. However, with 36 randomised patients, the study will have sufficient power to determine non-inferiority against standard-of-care based on data available in FBT in patients with C. dif. In two trials in non-critically ill patients, the success of FBT was 69% (22 out of 32) or 56% (5 out of 9) as compared to 45% cured by oral metronidazole. Assuming that clinically significant difference between the two methods is 20% and the intervention will be as effective in ICU patients as it was in the non-critically ill group (curing 27 out of 41, ie. 66%), if there is a true difference in favour of the experimental treatment of 21%, then 36 patients are required to be 80% sure that the upper limit of a one-sided 95% confidence interval (or equivalently a 90% two-sided confidence interval) will exclude a difference in favour of the standard group of more than 20%. The expected duration of participation in the study is 6 months.

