## Hypothesis and aims:

We hypothesise that FBT will be feasible as first-line treatment of postantibiotic diarrhoea in the critically ill, incl. those with uncomplicated C. dif. infection.

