# Secondary end-points are:

- Composite number of adverse events such as new-onset sepsis, toxic megacolon, positive post FBT blood culture, or other SAE assessed by the physician-in-charge as possibly related to FBT.
- SOFA score at days 4 and 7.
- Percentage of patients that are recurrence-free at time of hospital discharge or day 28, whichever occur earlier.
- Subgroup analysis will be performed for patients who are C. dif. positive vs. negative and those who will receive antibiotics for a new extraabdominal infection vs. those who do not.

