## Study subjects:

- Inclusion Criteria: All of the following: Informed consent (see below), Age > 18 yrs., In-patient in ICU or HDU (incl. burn unit) and expected to stay for >7 days, Diarrhoea following antibiotic treatment defined as 3 or more stools per day or Bristol type 7 stool in the volume >300 ml/day if stool derivative device is in place, persisting for 24 hours despite enteral feeding formula has been stopped.
- Exclusion criteria: Death appears imminent or ceilings of care put in place, presence of new-onset sepsis defined as per 2016 definition, lactate >2.0 mM, colon diameter > 9 cm on plain AXR, the necessity of ongoing antibiotic treatment for another reasons. Unable to tolerate enema for any reason (e.g. surgery of the GI tract in the past year). Pregnant and lactating woman. Patients with a history of severe anaphylactic food allergy, any other reason

22.9.2021 Protocol version 9.2

which — as per judgement of the treating clinician — makes faecal transplantation unsafe or not feasible (Note: All screening failures based on this criterion will be reported separately, inc. the reason why it was considered unsafe or not feasible to proceed).

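### The claim of 80% non-inferiority power at 36 patients rests on a 21-point advantage not documented for this trial's population or controls, and the statistical plan contains no matching test.

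*Combined protocol and SAP*

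**What the plan says.** The section on sample size plans 36 patients, 1:1, and calls the trial a pilot whose primary concern is feasibility and safety. It places the trial "in the population of critically ill adults with C. dif. positivity and diarrhoea". It then adds that "with 36 randomised patients, the study will have sufficient power to determine non-inferiority against standard-of-care".

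The inputs are FBT success in two trials of non-critically ill patients (22/32 and 5/9, pooled to 27/41 or 66%), "as compared to 45% cured by oral metronidazole". The 80% power is stated to apply "if there is a true difference in favour of the experimental treatment of 21" percentage points. The criterion is that a one-sided 95% limit, "or equivalently a 90% two-sided confidence interval) will exclude a difference in favour of the standard group of more than 20" percentage points.

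Other sections describe a different setting:

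- Study subjects requires "Diarrhoea following antibiotic treatment defined as 3 or more stools per day", or a volume criterion when a stool device is in place. C. dif. positivity is not required.
- Hypothesis and aims speaks of "first-line treatment of postantibiotic diarrhoea in the critically ill, incl. those with uncomplicated C. dif. infection".
- Under the secondary end-points, "Subgroup analysis will be performed for patients who are C. dif. positive vs. negative".
- Control group assigns waiting for spontaneous resolution, and vancomycin in the C. dif.-positive subset. No control patient is assigned metronidazole.
- Primary end-point is a binary status at day 7, and counts non-administration of the allocated treatment as failure.
- Statistical plan compares the primary outcome by an unadjusted hazard ratio with a 95% interval, per protocol. It gives no margin and no non-inferiority rule.

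**The concern.** A power statement is useful only if its population, comparator and criterion are those of the trial. Here each of the three differs from what the rest of the document describes.

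The sample size section says that the power is conditional on a 21-point advantage and names where the rates come from. It assumes openly that FBT will work as well in ICU patients as in the non-critically ill. It makes no corresponding argument that a metronidazole cure rate applies to waiting or to vancomycin, nor that either rate applies to C. dif.-negative patients.

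At stake is how a 36-patient result would be read. A reader could take the sample as adequate for a non-inferiority conclusion against standard of care, although the inputs are not shown to fit and the planned primary analysis does not test that conclusion.

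**Working it through.** **Inputs, all from the sample size section.** Control success ps = 0.45; FBT success pe = 0.66 (27/41 = 0.659); margin 0.20; one-sided 5% (z = 1.645); power 80% (z = 0.842); n = 18 per arm.

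**1. Reproduce the plan's figure.**

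n per arm = (1.645 + 0.842)² × [ps(1−ps) + pe(1−pe)] / (pe − ps + 0.20)²
= 6.185 × (0.2475 + 0.2244) / 0.41² = 17.4, so 18 per arm and 36 in total.

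SE of the difference = √(0.4719/18) = 0.1619.
Power = Φ(0.41/0.1619 − 1.645) = Φ(0.887) = 81%.

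Exact binomial enumeration, counting success when the lower 90% Wald limit for FBT minus control exceeds −0.20, gives 79%. The plan's number stands.

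**2. What the 80% depends on.** Keep the difference at 21 points and move the base rate, with 18 per arm:

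| Control / FBT success | Formula | Exact |
|---|---|---|
| 30% / 51% | 82% | 81% |
| 39.5% / 60.5% (lowest) | 80.8% | 78.6% |
| 45% / 66% | 81% | 79% |
| 50% / 71% | 82% | 81% |
| 60% / 81% | 87% | 87% |

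The base rate hardly matters. The size of the FBT advantage does.

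**3. Is the 21 points documented for this trial?**

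| | Source of the 21 points | This trial |
|---|---|---|
| Patients | Non-critically ill, C. dif. | ICU/HDU, any post-antibiotic diarrhoea |
| Control | Oral metronidazole, 45% | Waiting, or vancomycin if C. dif.-positive; no rate given |
| FBT | 66% | No rate given for C. dif.-negative patients |

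**4. Sensitivity to the advantage.** FBT is held at 66%, which is itself an assumption. Control rates other than 45% are also assumptions, because the documents give none.

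| Control success | Power, formula | Power, exact | n per arm for 80% (formula) |
|---|---|---|---|
| 30% | 97.5% | 96% | 9 |
| 40% | 89% | 87% | 14 |
| 45% (planned) | 81% | 79% | 18 |
| 50% | 72% | 70% | 23 |
| 60% | 49% | 49% | 43 |
| 66% | 35% | 36% | 70 |

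**5. Criterion against planned analysis.** The criterion is a difference in proportions, a 90% two-sided interval and a 20-point margin. The planned analysis is a hazard ratio with a 95% interval and no margin. A ratio does not fix a difference unless the control rate is known. Even for a simple ratio of failure risks, 20 points is 0.75/0.55 = 1.36 when control failure is 55%, but 0.54/0.34 = 1.59 when it is 34%. The planned interval therefore cannot be read against the stated margin. A per-protocol set could also remove patients whose treatment was not delivered, whom the primary end-point counts as failures.

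**6. Precision at 45% against 66%.** The 95% half-width for the difference is 1.96 × 0.1619 = 0.317, or about ±32 points.

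**The case against.** The strongest defence is disclosure. The section calls the trial a pilot, says the power is based on C. dif. data, names metronidazole and the non-critically ill source, and states the 21-point condition. The margin, interval level and direction are also written down, though not in the statistical plan. All of this stands, and it limits the fault to applicability and specification. It does not remove the fault: after the pilot statement the section goes on to assert sufficient power for the trial as a whole, and naming a source does not show that it applies.

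It can also be said that the choice of hazard ratio and analysis set is a separate analysis matter. That is fair as far as it goes. It belongs here only because a non-inferiority power claim needs a planned analysis that can test it.

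Four stronger readings are tempting, and the documents do not support them:

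- **The trial is underpowered.** The true control rate is not given. With FBT at 66%, power exceeds 80% if control success is below 45%.
- **The 80% holds only at exactly 45% against 66%.** Step 2 shows that any pair 21 points apart gives about 81% or more by formula, and about 79% or more exact.
- **The real power is 35%, or 140 patients are needed.** That case assumes no true FBT advantage. It is a different planning hypothesis, not a correction of the plan's own, and the fixed 66% is no better supported in an all-comer population than the 45%.
- **A 20-point margin is wrong against waiting, or the 66% ignores non-delivery.** The documents do not settle either question.

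**Conclusion.** The concern holds as one of support, not of arithmetic. The 36 patients follow correctly from the stated inputs. However, the population wording contradicts the eligibility criteria and the sections that treat C. dif. as a subset; the 21-point advantage on which the 80% depends is not documented for this trial's patients or controls; and the non-inferiority criterion is not carried into the statistical plan.

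The direction of any error in power is unknown. The range of 97.5% down to 35% by formula, for control success of 30% to 66%, is an illustration that rests on FBT success of 66% and on assumed control rates. The pilot and feasibility aim is unaffected. This should be fixed, because as written the plan claims power for a conclusion that its primary analysis cannot deliver.

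**What to change.** In the sample size section, change the population to match Study subjects: post-antibiotic diarrhoea, C. dif.-positive or negative. Then take one of two routes.

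1. **Withdraw the non-inferiority power claim.** Justify 36 as a pilot by precision, quoting a 95% interval for the difference of about ±32 points at 45% against 66%.
2. **Keep the claim, qualified and testable.** State that the 80% is conditional on a 21-point advantage not documented for waiting or vancomycin, and show how power changes in both directions. In the statistical plan, replace the hazard ratio with the day-7 risk difference and its 90% two-sided interval, read against the 20-point margin. Use an analysis set that keeps non-delivery as failure, as the primary end-point defines it.

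Neither route adds patients or procedures. The first rewrites one paragraph and gives up the claim. The second keeps a weaker claim and changes the effect measure, interval level and analysis set of the primary comparison.

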# Primary end-point:

• Percentage of patients with treatment failure at day 7 after randomisation. Treatment failure is defined as either failure to administer allocated treatment for any reason or the presence of diarrhoea on day 7 after randomisation (as assessed by personnel blinded to treatment allocation).

22.9.2021 Protocol version 9.2

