## Informed consent procedure:

[figure not shown]
All patients with capacity will be asked to provide a prospective written informed consent (See Appendix 3). For patients without capacity, a deferred consent procedure will take a place. In this case, an independent clinician will review and sign that the patient is lacking capacity and he/she fulfils all criteria to be enrolled to the

Unique Protocol ID: 2021-002290-25 22.9.2021 Protocol version 9.2

study. The patient's next of kin will be informed about the study as soon as practical with the aid of information leaflet (Appendix 3). The patient will be asked to provide and sign informed consent as soon as he/she regains the capacity to do so. In case of consent refusal, patient's data will not be used in per-protocol analysis.

22.9.2021 Protocol version 9.2

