# Statistical plan:

Safety parameters will be reported on intention-to-treat basis. Primary outcome will be compared by as unadjusted hazard ratio of not being cured (with 95% interval) in a per protocol analysis. The subset of patients with C. dif positivity will be analysed separately.

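### The 80% power claim treats all 36 randomised patients as analysed and uses a one-sided 95% limit; the planned per-protocol analysis with a 95% interval does not secure it

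*Combined protocol and SAP*

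**What the plan says.** The Sample study size section opens with "We plan to randomise 36 patients in 1:1 ratio". It calls the study a pilot, then adds that this number gives sufficient power for non-inferiority against standard of care. The inputs are FBT success carried over from non-critically ill patients ("curing 27 out of 41, ie. 66"%), a control rate given "as compared to 45% cured by oral metronidazole", and a 20-point margin on the difference in success. The criterion is the "upper limit of a one-sided 95% confidence interval (or equivalently a 90% two-sided confidence interval"). On these inputs, "then 36 patients are required to be 80% sure" of excluding the margin. No allowance for losses is stated.

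Three other sections bear on whether that figure applies:

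- Statistical plan: the primary outcome is compared as an "unadjusted hazard ratio of not being cured (with 95% interval) in a per protocol analysis". No non-inferiority margin appears there.
- Informed consent procedure: patients without capacity enter under deferred consent, and if consent is later refused the patient's "data will not be used in per-protocol analysis".
- Primary end-point: treatment failure includes "failure to administer allocated treatment for any reason", as well as diarrhoea on day 7.

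No rate of refusal or of non-delivery is given anywhere.

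**The concern.** The power statement and the analysis describe different things. The first counts every randomised patient and uses a one-sided 95% limit on a risk difference. The second is per protocol, foresees removal of some randomised patients, and reports a 95% interval on a hazard ratio. Rounding up to 18 per arm leaves a margin of less than one patient per arm, so even small losses matter to the claim as worded.

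At stake is how an inconclusive result is read. If the protocol says the trial was adequately powered for non-inferiority, a confidence limit that fails to exclude the margin may be taken as evidence against FBT, when the analysis never had the stated power.

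**Working it through.** **Inputs** (Sample study size): control success pC = 0.45; FBT success pT = 0.66 (27/41 = 0.659); margin M = 0.20; one-sided alpha 0.05; power 0.80; 18 per arm.

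**Reproducing the plan's figure.** Unpooled normal approximation:

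n per arm = [pC(1−pC) + pT(1−pT)] × (z₁₋α + z₀.₈₀)² / (M + pT − pC)²

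= (0.2475 + 0.2244) × (1.645 + 0.842)² / 0.41² = 17.36, rounded up to 18, so 36 in total. The plan's number is confirmed.

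**Power at a given evaluable number.** Power = Φ[(M + pT − pC)/SE − z₁₋α], with SE = √(0.4719/n).

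At n = 18, SE = 0.1619 and 0.41/0.1619 = 2.532. With z = 1.645, Φ(0.887) = 81.3%. With z = 1.960, Φ(0.572) = 71.6%.

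| Evaluable per arm (total) | One-sided 95% limit | Two-sided 95% interval |
|---|---|---|
| 18 (36) | 81.3% | 71.6% |
| 17 (34) | 79.3% | 69.2% |
| 16 (32) | 77.1% | 66.5% |
| 14 (28) | 72.2% | 60.8% |

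The totals below 36 are assumptions, since the documents give no loss rate. Exact enumeration of the Wald interval at 18 per arm gives 79.3% (one-sided 95%) and 69.2% (two-sided 95%), so the approximation is slightly generous. With the two-sided interval, 80% power would need 22.03, hence 23, per arm (46 in total).

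**Undelivered treatment counted as failure.** Let d be the assumed proportion undelivered, with all 36 analysed and the one-sided 95% limit. Success becomes 0.66(1−d) in the FBT arm and, if delivery also fails there, 0.45(1−d) in the control arm. Example with d = 0.10:

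- Both arms: 0.594 v 0.405. The numerator is 0.20 + 0.189 = 0.389 and SE = 0.1637, so Φ(0.732) = 76.8%.
- FBT arm only: 0.594 v 0.45. The numerator is 0.20 + 0.144 = 0.344 and SE = 0.1648, so Φ(0.443) = 67.1%.

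| Assumed non-delivery | Equal in both arms | FBT arm only |
|---|---|---|
| 5% | 79.0% | 74.6% |
| 10% | 76.8% | 67.1% |
| 20% | 72.9% | 51.1% |

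This table applies only if the 66% does not already include undelivered treatment. If undelivered FBT patients were excluded instead of counted as failures, the loss is smaller: 79.5% at 10% and 77.3% at 20%.

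**The case against.** The strongest reply is that the sentence is conditional on its inputs and correct on them, in a trial that calls itself a pilot and has feasibility as its hypothesis. Small losses also do little: one patient lost leaves 80.2% to 80.3%, and an assumed 5% loss in both arms leaves 79.5%. All of that stands. It limits the size of the point but does not remove it, because the protocol goes past the pilot label and claims sufficient power for 36 randomised patients.

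A reader might infer four stronger things that the documents do not support.

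- **That per protocol drops untreated patients as well as refusers.** The Statistical plan does not define the per-protocol set. Only refusers are removed by text, and the Primary end-point section counts non-administration as failure. Exclusion and counting as failure are alternatives and must not be added together.
- **That the 66% assumes full delivery.** The section gives only 22 of 32 and 5 of 9 successes. Whether those trials counted undelivered treatment as failure cannot be seen here. If they did, the non-delivery table would count it twice.
- **That power is as low as 51%.** This needs 20% non-delivery confined to the FBT arm. The end-point wording refers to allocated treatment without naming an arm, and equal rates at the same level give 73%. Neither pattern is documented.
- **That the decision certainly rests on a two-sided 95% interval.** The sample size section defines the criterion as a one-sided limit. The 95% interval in the Statistical plan belongs to a hazard ratio with no margin, and the plan does not say that it replaces that criterion. The two-sided column above is therefore a conditional reading.

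**Conclusion.** The concern holds in limited form. It would be wrong to call 36 a miscalculation; it reproduces exactly. The defect is that the 80% belongs to an analysis of all randomised patients on a one-sided limit, which the Statistical plan and the consent rule do not secure.

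The size depends on three things the documents leave open:

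- **Evaluable number:** from 81% with all 36 to 79% with one lost per arm, and 77% or 72% at assumed totals of 32 or 28.
- **Interval:** about 10 points lower at 36 (72%) if a two-sided 95% interval decides non-inferiority; no effect if the one-sided limit stands.
- **Non-delivery counted as failure:** at assumed rates of 5, 10 or 20%, 79, 77 or 73% if equal in both arms, or 75, 67 or 51% if in the FBT arm only, provided the 66% does not already include it.

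The feasibility aim does not depend on this power figure. The change is still worth making, because the non-inferiority claim is explicit.

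**What to change.** Keep 36 patients and change the text in three places.

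- **Statistical plan:** state that the non-inferiority decision uses the 20-point risk-difference margin and the one-sided 95% (two-sided 90%) limit from the Sample study size section.
- **Sample study size, power sentence:** replace it with power of about 81% if all 36 are evaluable, 77% at 32 and 72% at 28. Label the evaluable numbers as assumptions and note that power is lower if undelivered treatment counts as failure.
- **Sample study size, claim of sufficient power:** state that the non-inferiority comparison is supportive to the feasibility aim.

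The cost is a few sentences and a slightly less favourable power figure. No patients are added. If the sponsor intends a two-sided 95% interval for the decision, the figures to print are 72%, 66% and 61% at 36, 32 and 28 evaluable.
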